5.3.2 Barthel Index of Activities of Daily Living

The Barthel Index consists of 10 items that measure a person's daily functioning; specifically the activities of daily living and mobility.

The Barthel Index will be completed at Baseline (Visit 3) and Week 12/End of Treatment (Visit 6).

5.3.3 Vulnerable Elders Survey

The Vulnerable Elders Survey (VES-13) is a simple function-based tool for screening community-dwelling populations to identify older persons at risk for health deterioration.

The VES considers age, self-related health, limitation in physical function, and functional disabilities.

The Vulnerable Elders Survey will be completed at Baseline (Visit 3) and Week 12/End of Treatment (Visit 6).

5.3.4 Patient Perception of Intensity of Urgency Scale

The Patient Perception of Intensity of Urgency Scale (PPIUS) is a scale that will be completed as part of the micturition diary.

For each micturition and/or incontinence episode, subjects will be asked to rate the degree of associated urgency according to the following validated 5-point categorical scale. The categories are recommended by the Committee for Proprietary Medicinal Products [CPMP/EWP/18/01, Final].

- 0 – No urgency, I felt no need to empty my bladder, but did so for other reasons.
- 1 – Mild urgency, I could postpone voiding as long as necessary, without fear of wetting myself.
- 2 – Moderate urgency, I could postpone voiding for a short while, without fear of wetting myself.
- 3 – Severe urgency, I could not postpone voiding, but had to rush to the toilet in order not to wet myself.
- 4 – Urge incontinence, I leaked before arriving at the toilet.

5.3.5 OAB Symptoms, Quality of Life, Bladder Health and Treatment Benefit

OAB has significant effects on health-related quality of life (QoL) of the afflicted subjects. This has been quantified in various empirical studies [Wall et al, 1993]. QoL is determined by socio-demographic, clinical, psychological and social factors. This underlines the importance of assessing the perceptions of subjects themselves when evaluating the effects of medical or pharmacological treatment. This is done in QoL research, also in the OAB field [Palmtag 2004]. In this study, the Overactive Bladder-questionnaire (OAB-q), the Patient Perception of Bladder Condition (PPBC), TS-VAS, and University of Alabama – Birmingham Life Space Assessment (UAB-LSA) will be utilized.

5.3.5.1 Overactive Bladder-questionnaire

OAB symptoms and QoL in relation to OAB will be assessed by the Overactive Bladder Questionnaire (OAB-q) [Coyne et al, 2002]. This questionnaire has validated psychometric properties, has been used extensively in QoL-research in respondents with OAB, and has been shown to be responsive in treatment studies [Coyne et al, 2002]. The OAB-q is a self-reported questionnaire with 33 items, which contain the dimensions Coping, Concern, Sleep, Social Interaction, and a Symptom Bother scale with eight symptoms [Garely et al, 2007].

The OAB-q will be assessed at Baseline (Visit 3), Week 4 (Visit 4), Week 8 (Visit 5), and Week 12/End of Treatment (Visit 6).

5.3.5.2 Patient Perception of Bladder Condition

The Patient Perception of Bladder Condition (PPBC) is a validated, global assessment tool using a 6-point Likert scale that asks subjects to rate their subjective impression of their current bladder condition [Coyne et al, 2006]. The PPBC questionnaire will be assessed at Baseline (Visit 3), Week 4 (Visit 4), Week 8 (Visit 5), and Week 12/End of Treatment (Visit 6).

5.3.5.3 Treatment Satisfaction – Visual Analog Scale

The Treatment Satisfaction – Visual Analog Scale (TS-VAS) is a visual analog scale that asks subjects to rate their satisfaction with the treatment by placing a vertical mark on a line that runs from 0 (No, not at all) to 10 (Yes, completely). The TS-VAS will be assessed at Baseline (Visit 3), Week 4 (Visit 4), Week 8 (Visit 5), and Week 12/End of Treatment (Visit 6).

5.3.5.4 University of Alabama, Birmingham Life Space Assessment

The University of Alabama, Birmingham (UAB) Study of Aging Life-Space Assessment (LSA) measures mobility in terms of the spatial extent of a person's life. The purpose of the Life-Space Assessment is to determine a person's usual pattern of mobility during the month preceding the assessment. Life-space is defined based upon the distance a person routinely travels to perform activities over this time frame. The UAB-LSA includes determining how far and how often the person leaves his or her place of residence and the degree of independence the person has.

Each level of life-space represents a distance further from the room where one sleeps.

- 0 = Mobility limited to the room where one sleeps
- 1 = Mobility limited to within one's dwelling
- 2 = Mobility limited to the space just proximal to one's personal living space (for instance, a porch, patio, or yard just outside the home or hallway outside of an apartment)
- 3 = Mobility limited to one's neighborhood
- 4 = Mobility limited to one's town
- 5 = Mobility outside one's town

The UAB-LSA will be assessed at Baseline (Visit 3), Week 4 (Visit 4), Week 8 (Visit 5), and Week 12/End of Treatment (Visit 6).

5.4 Safety Assessment

The safety evaluations including vital signs, cognition, adverse event recording, clinical laboratory assessments and physical examination will be performed according to [Table 1](#) Schedule of Assessments.

Please review the requirements related to the evaluation, reporting and analysis of Drug-Induced Liver Injury (DILI) information found in [Appendix 2](#) (Liver Safety Monitoring and Assessment). In the event of a confirmed, marked hepatic abnormality as defined in [Appendix 2](#) it is the Investigator's responsibility to ensure contact with the Sponsor/delegated CRO by telephone or fax immediately (i.e., within 24 hours of awareness).

5.4.1 Vital Signs

Vital signs, including pulse rate and blood pressure, will be measured at all in-office visits according to [Table 1](#) Schedule of Assessments.

The patient should be seated comfortably for at least 5 minutes with the back supported, feet on the floor, arm supported in a horizontal position, and the blood pressure cuff at heart level for each blood pressure measurement. The Investigator will use the same device and cuff size throughout the study. The same arm should be used throughout the study.

An AE of hypertension will be recorded if one of the following criteria is met on 2 or more consecutive visits:

1. If the average systolic blood pressure is > 140 mmHg AND/OR the average diastolic blood pressure is > 90 mmHg at two consecutive visits after Baseline (Visit 3) in subjects who were normotensive (average systolic blood pressure < 140 mmHg and average diastolic blood pressure < 90 mmHg [WHO-ISH, 2003]) at Baseline (Visit 3).
2. If the average systolic blood pressure is increased > 20 mmHg AND/OR the average diastolic blood pressure is increased > 10 mmHg at two consecutive visits as compared to Baseline (Visit 3) in subjects with hypertension at Baseline (Visit 3).
3. If treatment with antihypertensive drugs is initiated for treatment of hypertension or if the dose of prior antihypertensive drugs is increased due to an increase in blood pressure.

An AE of "increased" Blood Pressure should be considered if the above conditions are not met, but a high blood pressure is recorded.

An AE of tachycardia should be considered if resting heart frequency (pulse rate) is > 100 bpm.

5.4.2 Patient Diary - Subject Measurement Vital Signs

During Visit 2 (Placebo Run-In), the Investigator should instruct the subject on how to perform and document in the electronic diary the self-measurement of BP and PR. The subject will have an opportunity to familiarize him/herself with the self-measurement of BP and PR and recording of the data.

Diaries for vital signs (measured at home) will be completed in both am and pm for 3 consecutive days prior to each visit: Baseline (Visit 3), Week 4 (Visit 4), Week 8 (Visit 5), and Week 12/End of Treatment (Visit 6).

Validated devices for measuring BP and PR will be provided to subjects along with detailed operating instructions. The Investigator should measure the circumference of the upper arm in order to give the subject the device with the correct cuff type (Adult: 25-35 cm; Adult Plus: 33-40 cm arm circumference).

At home, according to the “The ABCD’s of Blood Pressure Measurement” [American Heart Association, April 2012], the subject should rest for at least 5 minutes before taking the measurements. The subject should be quiet and relaxed, sitting in a chair with feet on the floor, legs should not be crossed, and arms should be bare and supported at heart level. The cuff should be put on according to the instructions of the Investigator. The subject should not move and should remain silent during the reading as moving and talking can affect the reading.

The subject should measure his/her BP and PR in triplicate during the 3 consecutive days prior to the next visit, on the arm chosen from the Screening measurements. Measurements should be taken after waking up in the morning and again in the evening. The subject should ensure that the morning measurements of vital signs are taken before breakfast and before study medication intake.

Three readings should be taken at every occasion, each about 2 minutes apart.

The subject should keep adequate records of the readings. Date, time, systolic and diastolic BP, and PR should be documented in the electronic diary. The subject should take care to have a 30 minute rest after exercise or smoking or intake of caffeine or alcohol, prior to taking a measurement.

An AE of tachycardia should be reported if the mean am or pm PR in the resting state from subject reported measurements at home over the last 3 diary days is >100 bpm.

5.4.3 Montreal Cognitive Assessment

Montreal Cognitive Assessment (MoCA) will be assessed at Baseline (Visit 3) and Week 12/End of Treatment (Visit 6).

The MoCA was designed as a rapid screening instrument for mild cognitive dysfunction. It assesses different cognitive domains: attention and concentration, executive functions, memory, language, visuoconstructional skills, conceptual thinking, calculations, and orientation. Time to administer the MoCA is approximately 10 minutes. The total possible score is 30 points [Nasreddine et al, 2005].

5.4.4 Adverse Events

AE collection will begin from the time of informed consent and continue through the Follow-up Phone Call (Visit 7/Week 16). See **Section 5.5 Adverse Events and Other Safety Aspects** for information regarding adverse event collection and data handling.

5.4.4.1 Adverse Events of Possible Hepatic Origin

See [Appendix 2 Liver Safety Monitoring and Assessment](#) for detailed information on liver abnormalities, monitoring and assessment, if the AE for a subject enrolled in a study and receiving study drug is accompanied by increases in liver function testing (LFT, e.g.: AST, ALT, bilirubin, etc.) or is suspected to be due to hepatic dysfunction.

Subjects with AEs of hepatic origin accompanied by Liver Function Test (LFT) abnormalities should be carefully monitored.

5.4.5 Laboratory Assessments

Below is a table of the laboratory tests that will be performed during the conduct of the study.

See [Table 1 Schedule of Assessments](#) for study visit collection dates. For this study, a Central Lab will be used for all laboratory assessments.

Table 3 Laboratory Assessments

Screening (Visit 1) Week 12/End of Treatment (Visit 6)	Hematology	CBC Hemoglobin Hematocrit
Screening (Visit 1) Week 12/End of Treatment (Visit 6)	Chemistry	Sodium Potassium Calcium Chloride Glucose Creatinine Alkaline phosphatase AST ALT GGT Total bilirubin Total protein Albumin INR
Screening (Visit 1) Week 12/End of Treatment (Visit 6)	Urinalysis	Protein Glucose pH Blood Urine Culture*

* Urine culture and sensitivity will be performed for positive leukocytes, or nitrites, or turbidity, or at the discretion of the PI.

Clinical significance of out-of-range laboratory findings is to be determined and documented by the Investigator/sub-Investigator who is a qualified physician.

5.4.6 Physical Examination

The subject will have a physical examination performed at Screening (Visit 1) and Week 12/End of Treatment (Visit 6). This includes examination of main body systems. Date

of physical examination and any clinically relevant adverse changes will be recorded as an AE in the eCRF (see Section 5.5.1).

5.4.7 Electrocardiogram (ECG)

A 12-lead ECG will be recorded at Screening (Visit 1), the Placebo Run-In (Visit 2), Baseline (Visit 3), Week 4 (Visit 4), Week 8 (Visit 5), and Week 12/End of Treatment (Visit 6). ECGs will be taken with the subject in the sitting or supine position. The patient's sitting or supine position for the ECG should be consistent throughout the course of the study.

All tracings will be read locally by the Investigator to ensure patient safety and care management. Any abnormalities must be evaluated in clinical context (based on subject's medical history and concomitant medication) and the Investigator must determine if it is clinically significant. Clinically significant abnormalities must be reported as an AE.

5.4.8 Post-Void Residual Volume

Post-Void Residual (PVR) volume will be assessed by ultrasonography or bladder scan at Screening (Visit 1) and Week 12/End of Treatment (Visit 6).

5.4.9 Cough Provocation Test

The cough provocation test will be performed for female subjects at Screening (Visit 1). Female subjects will be asked to come to the clinic with a comfortably full bladder. With the subject in the supine position, the volume of urine in the bladder is measured by ultrasound. The bladder volume must exceed 100 mL for the assessment of stress incontinence. Subsequently the subject will be asked to cough vigorously in the standing position. An immediate loss of urine will confirm a clinical diagnosis of stress incontinence [Wall et al, 1993].

5.4.10 Follow-up Phone Calls to Patient

Subjects will be contacted 4 weeks after End of Treatment (Visit 6/Week 12) by telephone for a Follow-up Phone Call (Visit 7/Week 16) to assess concomitant medication and any adverse events that may have occurred following the end of treatment.

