Serious Adverse Event	An adverse event is considered "serious" if, in the view of either the Investigator or Sponsor, it results in any of the following outcomes: results in death, is life threatening, results in persistent or significant disability/incapacity or substantial disruption of the ability to conduct normal life functions, results in congenital anomaly, or birth defect, requires inpatient hospitalization or leads to prolongation of hospitalization, or a medically important event.
Stress urinary incontinence	The complaint of involuntary leakage on effort or exertion, or on sneezing or coughing.
Subject number	Number assigned to each subject by Interactive Response System after signature of informed consent and prior to any specific procedures.

Terms	Definition of terms
Treatment-emergent adverse event	An adverse event starting or worsening in the period from first double-blind medication intake until 30 days after last double-blind medication intake.
Urgency	A sudden and compelling desire to pass urine that is difficult to defer.
Urgency urinary incontinence	The complaint of involuntary leakage accompanied by or immediately proceeded by urgency.
Urinary incontinence	The complaint of any involuntary leakage of urine.

IV. SYNOPSIS

Title of Study	A Phase 4, Double-Blind, Randomized, Placebo-Controlled, Parallel Group, Multi-Center Study to Evaluate the Efficacy, Safety, and Tolerability of Mirabegron in Older Adult Subjects with Overactive Bladder (OAB)
Planned Study Period	From 3Q2014 to 4Q2016
Study Objective(s)	
Primary Objective: To assess the efficacy of mirabegron versus placebo (PBO) in the treatment of older adult subjects with OAB.
 
Secondary Objective: To assess the safety and tolerability of mirabegron versus placebo (PBO) in the treatment of older adult subjects with OAB.

Planned Total Number of Study Centers and Location	Approximately 125 centers North America (possibly to include South America, Europe, Australia, and/or Asia Pacific)

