--	--

	
Analysis on Secondary Endpoints The change from baseline to end of treatment for other secondary endpoints (excluding mean voided volume [MVV]) will be analyzed using a similar ANCOVA model as described above for mean number of micturitions per 24 hours. The change from baseline to end of treatment in MVV will be analyzed using the Stratified Rank ANCOVA and ANCOVA model as described above for mean number of incontinence episodes.
 
Safety: Safety analyses will be performed on the Safety Analysis Set (SAF) defined as all subjects who receive at least one dose of double-blind medication. Number and percentage of treatment-emergent adverse events reported during the double-blind period will be summarized by system organ class, preferred term, seriousness, severity, and relationship to treatment, overall and by treatment group.
 
Statistical differences in change from baseline to end of treatment in cognitive assessment will be tested using a paired sample Wilcoxon test.
 
Changes from baseline for PVR and laboratory assessments (biochemistry and hematology) will be summarized in tables by treatment group and visit.
 
Vital sign data will be analyzed separately based on the 3-day diary and the site assessment at each clinic visit. Change from baseline in vital sign variables will be analyzed using the same ANCOVA model as described for the analysis of change from baseline in mean number of micturitions per 24 hours. No p-values will be calculated.
 
ECGs will be performed at Screening (Visit 1), the placebo run-in period (Visit 2), Baseline (Visit 3), Week 4 (Visit 4), Week 8 (Visit 5), and Week 12/End of Treatment (Visit 6).
 
Interim Analysis: N/A

--	--

V. FLOW CHART AND SCHEDULE OF ASSESSMENTS

Figure 1 Flow Chart

[figure not shown]

Table 1 Schedule of Assessments

	Screening	Placebo Run-In	Treatment Period				Follow-up Phone Call
			1	2	3	4	
Visit	1	2	3	4	5	6	7
Day	-28	-14	1	28	56	84	112
Week	-4	-2	0/Baseline	4	8	12/EOT	16
Visit Windows (Days) ^a	+/- 10	+/- 3	+/- 3	+/- 7	+/- 7	+/- 7	+/- 3
Informed Consent/HIPAA	X						
Inclusion/Exclusion Criteria	X		X				
Medical History and OAB History	X						
Demographics	X						
Enter 2-week Placebo Run-in ^b		X					
Randomization ^c			X				
Physical Exam (including height ^d and weight)	X						X
Vital Signs – in office (includes pulse and blood pressure)	X	X	X	X	X	X	
Cough Provocation test (Females only)	X						
Serum chemistry, hematology & urinalysis ^e	X						X

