███████████ ^f	X						
12-Lead ECG	X	X	X	X	X	X	
Ultrasound or Bladder Scan (PVR)	X						X
Medication History and OAB Medication History	X		X				
Clinical Assessment for Dose Increase				X	X		
Concomitant Medications Assessment	X	X	X	X	X	X	X
Adverse Event Assessment		X	X	X	X	X	X
Dispense Study Drug		X	X	X	X		
Drug Accountability			X	X	X	X	
Instruct Subject on 3-day Micturition Diary ^g		X	X	X	X	X	
Complete 3-day Micturition Diary including vital sign measurements and PPIUS ^{h,i}			X ^h	X ^h	X ^h	X ^h	
OAB-q			X	X	X	X	
Patient Perception of Bladder Condition Scores (PPBC)			X	X	X	X	
TS-VAS			X	X	X	X	
Montreal Cognitive Assessment Test (MoCA)			X				X
Univ Alabama Birmingham Life Space Assessment (UAB -LSA)			X	X	X	X	

Table continues on next page

	Screening	Placebo Run-In	Treatment Period				Follow-up Phone Call
Visit	1	2	3	4	5	6	7
Day	-28	-14	1	28	56	84	112
Week	-4	-2	0/Baseline	4	8	12/EOT	16
Visit Windows (Days) ^a	+/- 10	+/- 3	+/- 3	+/- 7	+/- 7	+/- 7	+/- 3
Barthel ADL Assessment			X			X	
Vulnerable Elders Survey 13 (VES-13)			X			X	
Review Subject Diary ^j			X	X	X	X	

- a. Visits 1 and 2 are negatively scheduled from the Baseline (Visit 3) date. A subject has a combined timeframe of up to 38 days to complete both Visits 1 and 2; however, Baseline (Visit 3) must occur at least 18 days but no more than 38 days after Visit 1 (Screening) and at least 11 days but no more than 17 days after Visit 2 (Placebo Run-In). After Visit 2 (Placebo Run-In), visit windows/study days will be calculated based on the Visit 3 (Baseline) visit date. Study procedures (e.g. bladder scan) for a particular visit do not need to be completed on the visit date if this is not feasible for the subject, as long as, study procedures are performed per protocol within the applicable visit window. Any procedure not done or performed outside the applicable visit window will be noted as a protocol deviation.
- b. Subjects must take at least 11 days, but no more than 17 days of placebo run-in medication.
- c. Randomization is to occur after confirming all eligibility criteria and after performing all other visit procedures at Visit 3.
- d. Height will only be assessed at the Screening Visit.
- e. Urine culture and sensitivity will be performed for positive leukocytes, or nitrites, or turbidity, or at the discretion of the PI. If a subject has a UTI, the subject can be rescreened after successful treatment of the UTI (confirmed by a laboratory result of negative urine culture).

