2 FLOW CHART AND VISIT SCHEDULE

[figure not shown]

Table 1 Schedule of Assessments

	Screening	Placebo Run-In	Treatment Period				Follow-Up Call
Visit	1	2	3	4	5	6	7
Day	-28	-14	1	30	60	90	120
Week	-4	-2	0/BL	4	8	12/EoT	16
Visit Window (Days) ^a	+/- 10	+/- 3	+/- 3	+/- 7	+/- 7	+/- 7	+/- 3
Informed Consent/HIPAA	X						
Inclusion/Exclusion Criteria	X		X				
Medical History and OAB History	X						
Demographics	X						
Enter 2-week Placebo Run-in ^b		X					
Randomization ^c			X				
Physical Exam (including height ^d and weight)	X					X	
Vital Signs (includes pulse and blood pressure)	X	X	X	X	X	X	
Cough Provocation test (Females Only)	X						
Serum Chemistry, hematology, & urinalysis	X					X	
██████████	████						
12-Lead ECG	X	X	X	X	X	X	
Ultrasound or Bladder Scan (PVR)	X					X	

Table continues on next page							
	Screening	Placebo Run-In	Treatment Period				Follow-Up Call
Medication History and OAB Medication History	X		X				
Visit	1	2	3	4	5	6	7
Day	-28	-14	1	30	60	90	120
Week	-4	-2	0/BL	4	8	12/EoT	16
Visit Window (Days) ^a	+/- 10	+/- 3	+/- 3	+/- 7	+/- 7	+/- 7	+/- 3
Clinical Assessment for Dose Increase				X	X		
Concomitant Medications Assessment	X	X	X	X	X	X	X
Adverse Event Assessment		X	X	X	X	X	X
Dispense Study Drug		X	X	X	X	X	
Drug Accountability			X	X	X	X	
Instruct Subject on 3-day Micturition Diary ^f	X	X	X	X	X	X	
Complete 3-day Micturition Diary including PPIUS ^g			X ^h	X ^h	X ^h	X ^h	
OAB-q			X	X	X	X	
Patient Perception of Bladder Condition Scores (PPBC)			X	X	X	X	
TS-VAS			X	X	X	X	
Montreal Cognitive Assessment Test (MoCA)			X			X	

Table continues on next page

	Screening	Placebo Run-In	Treatment Period				Follow-Up Call
University of Alabama Birmingham Life Space Assessment (UAB-LSA)			X	X	X	X	
Barthel ADL Assessment			X			X	
Vulnerable Elders Survey 13 (VES-13)			X			X	
Review Subject Diary ⁱ			X	X	X	X	

- a. After Visit 2 (Placebo Run-In), visit windows/study days will be calculated based on the Visit 3 (Baseline) visit date.
- b. Subjects must take at least 11 days, but no more than 17 days of placebo run-in medication.
- c. Randomization is to occur after confirming all eligibility criteria and after performing all other visit procedures at Visit 3.
- d. Height will only be assessed at the Screening Visit.
- e. [REDACTED]

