6.2 Safety Variables

Safety will be assessed by evaluation of the following variables:

- Treatment-emergent adverse events (TEAEs; frequency, severity, seriousness, and relationship to study drug).
- Adverse Events of Possible Hepatic Origin (See [Appendix 1](#))
- Acute Urinary Retention
- Urinary Tract Infections
- Clinical laboratory variables (hematology, biochemistry including liver function tests, and urinalysis)
- Cardiovascular events, vital signs (systolic and diastolic blood pressure and pulse rate), MI, Stroke and serious arrhythmias.
- Montreal Cognitive Assessment (See [Appendix 5](#))
- Physical Examination
- 12-lead electrocardiogram (ECG)
- Post-Void Residual Volume

TEAE is defined as an adverse event observed after starting administration of the test drug/comparative drug. If the adverse event occurs on Day 1 and the onset check box is marked “Onset after first dose of study drug” or the onset check box is left blank, then the adverse event will be considered treatment emergent. If the adverse event occurs on Day 1 and the onset check box is marked “Onset before first dose of study drug”, then the adverse event will not be considered treatment emergent. If a subject experiences an event both during the pre-investigational period and during the investigational period, the event will be considered as a TEAE only if it has worsened in severity (i.e. it is reported with a new start date). All adverse events collected that begin within 30 days after taking the last dose of study drug will also be counted as TEAEs.

A drug-related TEAE is defined as any TEAE with possible or probable relationship to study treatment as assessed by the investigator or with missing assessment of the causal relationship.

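### TEAEs are counted to 30 days after the last dose, but scheduled AE collection ends at a call nominally 28 days after End of Treatment, and the documents do not settle what that call is anchored to

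*Protocol*

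**What the plan says.** - **TEAE period.** The Protocol's List of Key Study Terms runs it from the first double-blind intake "until 30 days after last double-blind medication intake". SAP 6.2 has the same length: "All adverse events collected that begin within 30 days after taking the last dose of study drug will also be counted as TEAEs".
- **End of collection.** Protocol 5.4.4: "AE collection will begin from the time of informed consent and continue through the Follow-up Phone Call (Visit 7/Week 16". Table 1 schedules no other contact after Visit 6.
- **Timing of the call in the text.** Protocol 5.4.10: "Subjects will be contacted 4 weeks after End of Treatment (Visit 6/Week 12) by telephone for a Follow-up Phone Call (Visit 7/Week 16". The reference point here is End of Treatment.
- **Timing of the call in the schedule.** The target-day row of Protocol Table 1 reads "Day -28 -14 1 28 56 84 112". The last two entries are Visit 6 (+/- 7 days) and Visit 7 (+/- 3 days). Footnote a says: "After Visit 2 (Placebo Run-In), visit windows/study days will be calculated based on the Visit 3 (Baseline) visit date". The reference point here is Baseline.
- **SAP schedule.** The same row in SAP Section 2 reads "Day -28 -14 1 30 60 90 120", with the same windows. SAP 7.10.3.1 repeats Day 120 as the target for the call but enters EOT+14 as the actual assessment day.
- **Early stoppers.** Protocol 6.1 provides follow-up for ongoing adverse events and unresolved laboratory results. It gives no date for the call.

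**The concern.** A TEAE table headed by a 30-day rule implies that subjects were asked about events for 30 days after their last dose. Here the last planned enquiry is set at 28 days, and the windows let it come earlier. Safety and tolerability is the secondary objective, and the TEAE summaries are central to reporting it. If the call comes before day 30, a late-onset event enters the count only if the site hears of it some other way. Two subjects with the same experience can then contribute different lengths of observation because of diary dates alone. The cardiovascular and neoplasm committees adjudicate events occurring in the study, so an event after an early call might not reach them.

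**Working it through.** **Inputs.** Visit 6 target T6 = 84 with d6 from -7 to +7; Visit 7 target T7 = 112 with d7 from -3 to +3 (Protocol Table 1). TEAE period 30 days (Key Study Terms; SAP 6.2). The last dose is taken to fall on the Visit 6 day, which is an assumption; the day before is run as a variant.

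**Formula.** Gap = (T7 + d7) - (T6 + d6). Uncovered days = max(0, 30 - gap).

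**1. The plan's own figure.** 112 - 84 = 28 days, which reproduces the 4 weeks of 5.4.10. Uncovered on target: 30 - 28 = 2 days.

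**2. Call tied to End of Treatment (5.4.10, with Table 1's +/- 3).** The gap is 28 +/- 3, or 25 to 31 days. Days 25 to 29 fall short: 5 of the 7 permitted days (71%), by 1 to 5 days.

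**3. Both windows run from Baseline (footnote a).** Visit 6 falls on Days 77 to 91 and the call on Days 109 to 115.
- Shortest gap: 109 - 91 = 18 days, leaving 30 - 18 = 12 uncovered.
- Longest gap: 115 - 77 = 38 days, leaving none uncovered.
- Full cover needs d7 - d6 of at least 2. For d7 = -3, -2, ..., 3 this holds for 3, 4, 5, 6, 7, 8 and 9 values of d6, a total of 42.
- There are 15 x 7 = 105 combinations, so 105 - 42 = 63 (60%) fall short. The mean over all 105 is 3.1 uncovered days.

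**4. Variants.** The last column treats every permitted day as equally likely.

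| Schedule and anchor | Last dose | Earliest / target / latest gap (days) | Before day 30 |
|---|---|---|---|
| Protocol, Baseline | Visit 6 day | 18 / 28 / 38 | 60% |
| Protocol, Baseline | day before | 19 / 29 / 39 | 53% |
| Protocol, End of Treatment | Visit 6 day | 25 / 28 / 31 | 71% |
| Protocol, End of Treatment | day before | 26 / 29 / 32 | 57% |
| SAP (Day 90, Day 120), Baseline | Visit 6 day | 20 / 30 / 40 | 47% |
| SAP (Day 90, Day 120), Baseline | day before | 21 / 31 / 41 | 40% |
| SAP, End of Treatment | Visit 6 day | 27 / 30 / 33 | 43% |

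**5. The SAP's EOT+14 entry.** Read as 14 days after End of Treatment, it matches neither the Protocol's 28-day gap nor the SAP's own 120 - 90 = 30.

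**6. Early stoppers.** Suppose the last dose and the End of Treatment visit both fall on Day 56 (illustration only). A Baseline-anchored call then comes 109 - 56 = 53 to 115 - 56 = 59 days later. A call tied to End of Treatment comes 25 to 31 days later. The choice of anchor decides whether the TEAE period is covered.

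**The case against.** The strongest reply is that this is a 28-versus-30-day wording mismatch. Section 5.4.10 is the specific provision and ties the call to End of Treatment, so the shortfall would be 2 days on target and 5 at most. The 18-day gap needs footnote a to prevail, with Visit 6 at its latest day and the call at its earliest. The SAP schedule closes the on-target gap altogether. SAP 6.2 counts only events that were collected, so it can be run as an attribution limit and does not promise 30 days of observation. AEs are summarised without inferential comparison (Protocol 7.5, SAP 7.5), and Protocol 1.3.1 describes pulse and blood pressure changes as reversible on stopping.

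Much of this stands, and it rules out several stronger readings that a reader might infer:
- **That the call always comes by day 28.** It does not. Day 28 is the target, and the Baseline-anchored windows run to day 38.
- **That most subjects are under-observed.** The documents give no distribution of visit or last-dose dates. The percentages above count permitted days, not subjects. Under a Baseline anchor, early stoppers have longer gaps.
- **That late SAEs are lost.** Protocol 5.5.5 requires SAE reporting within 24 hours of awareness and states no cut-off at Visit 7. Section 5.5.6 covers a new SAE arising during follow-up of an existing event. What is missing is active enquiry of a subject with no ongoing event.
- **That the treatment comparison is biased.** The scheduling rule is the same in both arms.

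The reply does not remove the mismatch. Under either Protocol anchor, with the last dose at Visit 6, the on-target call precedes the end of the TEAE period. The SAP schedule still permits gaps down to 20 days.

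**Conclusion.** The point holds as an inconsistency worth correcting, with a modest effect. The stated TEAE period is 2 days longer than scheduled collection when both contacts are on target under the Protocol. Across the windows the uncovered part reaches 5 days under the End of Treatment anchor and 12 under the Baseline anchor. Which anchor governs is unresolved, and the SAP adds a second schedule and an entry that fits neither. The likely consequence is some under-ascertainment of late-onset events and unequal follow-up between subjects, common to both arms. The day ranges rest on the last dose falling on the Visit 6 day. The 60% rests, in addition, on all in-window combinations being equally likely.

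**What to change.** Reconcile Protocol Table 1, 5.4.4 and 5.4.10, and the SAP schedule (Section 2), 6.2 and 7.10.3.1, with the TEAE definition. The simplest way is to time the existing call from the actual last-dose date, for subjects who stop early as well as completers. Give it a one-sided window that opens no earlier than the end of the 30-day period already defined. State one anchor in both documents and replace the EOT+14 entry accordingly.

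If the call is not moved, align the TEAE definition with the period actually observed and report the length of post-treatment follow-up by arm.

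The cost is wording in both documents. No visit or call is added; last-subject-out moves by a few days.
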